Patients that require *initiation* of antiretroviral treatment *prior to study month 7* and completion of all three quadrivalent HPV vaccinations will be taken off study and will not count towards the accrual ceiling for Cohort 2. Up to 10 additional patients will be allowed to enroll in Cohort 2 as replacements to reach the intended Cohort 2 N= 35. Patients that require *initiation* of antiretroviral treatment *after study month 7* following completion of all three quadrivalent HPV vaccinations will be allowed to remain on study.

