3.7 OFF TREATMENT AND OFF STUDY CRITERIA

- Off Treatment- Any Grade III or higher toxicity possibly or probably related to vaccine that does not resolve to baseline within 4 weeks with appropriate intervention.
- Off Treatment- Any Grade IV toxicity unrelated to vaccine that does not resolve to within grade 1 or lower within 8 wks.
- Off Treatment- Severe or life-threatening immediate hypersensitivity reactions following receipt of quadrivalent HPV vaccine.
- Off Treatment and Off Study- Development of an acute life-threatening condition or cancer.
- Off Treatment and Off Study- Inability to adhere to HAART.
- Off Treatment and Off Study- Discontinuation of HAART for >6 wks due to antiretroviral toxicity.
- Off Treatment- > 30% decrease in baseline CD4 cell count or percent or decrease in absolute CD4 count to < 350 cells/mm³ confirmed by at least 2 measurements 4 weeks apart.
- Off Treatment- Increase in HIV-1 RNA levels to > 100,000 copies/ml confirmed by at least 2 measurements 4 weeks apart.
- Off Treatment- Pregnancy. Patients will be taken off-study and advised to defer completion of their vaccination regimen until resolution of the pregnancy. Patients will also be reported to the Merck Pregnancy Registry [contact]) that monitors fetal outcomes of pregnant women exposed to GARDASIL®.
- Off Study- Non-compliance with study protocol evaluations and visits.
- Off Study- Study discontinuation at the request of the patient or at the discretion of the Principal Investigator or Lead Associate Investigator if they determine that study withdrawal is in the patient's best interest.

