5 DATA COLLECTION AND EVALUATION

5.1 DATA COLLECTION

The PI will be responsible for overseeing entry of data into an in-house password protected electronic system C3D and ensuring data accuracy, consistency and timeliness. The principal investigator, associate investigators/research nurses and/or a contracted data manager will assist with the data management efforts. All data obtained during the conduct of the protocol will be kept in secure network drives or in approved alternative sites that comply with NIH security standards. Primary and final analyzed data will have identifiers so that research data can be attributed to an individual human subject participant.

All adverse events, including clinically significant abnormal findings on laboratory evaluations, regardless of severity, will be followed until return to baseline or stabilization of event. Patients will be followed for adverse events for 30 days after removal from study treatment or until off-study, whichever comes first.

An abnormal laboratory value will be recorded in the database as an AE **only** if the laboratory abnormality is characterized by any of the following:

- Results in discontinuation from the study
- Is associated with clinical signs or symptoms
- Requires treatment or any other therapeutic intervention
- Is associated with death or another serious adverse event, including hospitalization.
- Is judged by the Investigator to be of significant clinical impact
- If any abnormal laboratory result is considered clinically significant, the investigator will provide details about the action taken with respect to the test drug and about the patient's outcome.

End of study procedures: Data will be stored according to HHS, FDA regulations and NIH Intramural Records Retention Schedule as applicable.

Loss or destruction of data: Should we become aware that a major breach in our plan to protect subject confidentiality and trial data has occurred, the IRB will be notified.

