6.7 ACCRUAL STOPPING RULE

Accrual to the HIV-infected cohorts (Cohort 1 and Cohort 2) will be halted if 3 or more patients within a given cohort or 5 or more total patients between the two cohorts are removed from the study before month 12 for a decline in CD4 count (3.9.7) and/or an increase in HIV-1 RNA levels (3.9.8) as outlined in section 3.9 Off-Treatment/Off-Study Criteria. Occurrence of these events prior to study month 12 would be suggestive of potential excess virologic safety risk possibly related to HPV vaccination, while their occurrence after study month 12 is most likely to be due to the emergence of antiretroviral resistance (Cohort 1 on HAART) or the natural history of the disease within an individual (Cohort 2 on no treatment). Study month 12 was the cutoff chosen for this stopping rule as it includes 12 months of observation following the first HPV vaccination and 6 months of observation following completion of the vaccination series (3 vaccine doses) at study month 6. In the event that accrual to the study is halted, the IRB will be consulted to determine whether the halt on enrollment should be permanent or can be addressed through an amendment to the protocol.

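### The accrual stopping rule in 6.7 counts removals from the study, but the CD4 and HIV-1 RNA criteria in 3.7 only stop treatment, so confirmed events between about months 7 and 12 can go uncounted

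*Combined protocol and SAP*

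**What the plan says.** Section 6.7 sets the trigger at 3 or more patients in Cohort 1 or Cohort 2, or 5 or more across the two, who "are removed from the study before month 12 for a decline in CD4 count (3.9.7) and/or an increase in HIV-1 RNA levels (3.9.8"). It gives its reason: "Occurrence of these events prior to study month 12 would be suggestive of potential excess virologic safety risk". It justifies the month-12 cutoff partly because that leaves six months of observation after the third dose.

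The body and table of contents have no section 3.9; section 3 ends at 3.8. The matching criteria are the 7th and 8th bullets of 3.7:

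- CD4: "Off Treatment- > 30% decrease in baseline CD4 cell count or percent or decrease in absolute CD4 count to < 350" cells/mm³, confirmed by two measurements 4 weeks apart.
- HIV-1 RNA: "Off Treatment- Increase in HIV-1 RNA levels to > 100,000 copies/ml confirmed by at least 2 measurements 4 weeks apart".

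The same list uses a different label where it means both consequences, for example "Off Treatment and Off Study- Inability to adhere to HAART". Section 5.1 also treats the two as separate events: "Patients will be followed for adverse events for 30 days after removal from study treatment or until off-study, whichever comes first".

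Section 3.3.1 governs ART changes. A Cohort 1 patient who changes ART, or a Cohort 2 patient who starts it, after month 7 and "following completion of all three quadrivalent HPV vaccinations will be allowed to remain on study". A Cohort 2 patient who starts it earlier "will be taken off study and will not count towards the accrual ceiling for Cohort 2"; Cohort 1 has the parallel rule.

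**The concern.** The event that 6.7 counts is not the event that 3.7 produces. Meeting the CD4 or RNA criterion stops vaccination. Nothing in either bullet takes the patient off study, and after month 7 section 3.3.1 expressly keeps on study those whose ART is then started or changed. By then there is usually no dose left to withhold, so meeting the criterion changes nothing that a count of removals would register.

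This matters because 6.7 is the plan's only numerical halt for possible vaccine-related HIV progression, and 7.5.1 provides neither a monitoring board nor an independent monitor. The study team applies the rule itself, so the wording should give one count. As written, a literal reader and a purposive reader can reach different totals from the same patients, and only one of them would stop enrolling.

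**Working it through.** The plan states no event rate, error rate or stopping probability for 6.7, so there is no figure to reproduce. The check is mainly of the text.

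**1. Which criteria are meant.** The cited items 3.9.7 and 3.9.8 correspond in order and content to bullets 7 and 8 of 3.7. The citation is stale numbering. Correcting it still leaves a count of removals attached to criteria labelled as treatment stops.

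**2. What happens to a patient who meets a criterion.**

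| Timing | Text that applies | Counted as removed? |
|---|---|---|
| Starts or changes ART before month 7, series incomplete | 3.3.1: off study, replaced | Not stated; arguably yes if the reason was CD4 or RNA |
| Starts or changes ART after month 7, all doses given | 3.3.1: remains on study | No, read literally |
| No ART start or change | 3.7: treatment stop only | No, read literally |

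**3. Constructed example, Cohort 2.** Patient A exceeds 100,000 copies/ml at month 3, is confirmed at month 4, starts ART and leaves under 3.3.1. Patients B and C exceed it at month 7, are confirmed at month 8, start ART and stay on study under 3.3.1.

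- Met a confirmed criterion before month 12: 1 + 2 = 3. The threshold of 3 is reached and accrual halts.
- Removed from the study: A only, so 1 (0 if A is not counted). No halt.

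The conclusion does not depend on how A is treated.

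**4. Sensitivity of the rule to undercounting (illustration only).** Assume 35 patients per cohort, all followed to month 12, independent, with the same risk p of meeting a criterion, and a fraction c of events counted. Both p and c are assumptions. With X ~ Binomial(35, cp) in each cohort, the chance of reaching the threshold is 1 − [P(X ≤ 2)]². The pooled limit adds nothing, because at most 2 + 2 = 4 is below 5.

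At p = 5%, c = 1: P(X ≤ 2) = 0.1661 + 0.3059 + 0.2737 = 0.7457, and 1 − 0.7457² = 0.444.

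| p | c = 1 | c = 0.5 | c = 0.25 |
|---|---|---|---|
| 2% | 0.064 | 0.010 | 0.001 |
| 5% | 0.444 | 0.110 | 0.019 |
| 10% | 0.906 | 0.444 | 0.110 |

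For scale, the cohort threshold is 3/35 = 8.6%. These are chances of ever reaching the threshold, not of halting in time, and they ignore replacements.

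**The case against.** The best defence is that the intended rule can be read out of the text. Section 6.7 refers to the criteria list as covering both off-treatment and off-study, speaks of the occurrence of events, and includes months in which no dose remains to be stopped. The labels in 3.7 are also used loosely: the pregnancy bullet carries the treatment-stop label yet takes the patient off study. Much of this stands, and a sensible team might count correctly. But the pregnancy bullet does so through an added sentence that the CD4 and RNA bullets lack, and the permission in 3.3.1 to stay on study is express.

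A reader might infer four stronger things that the documents do not support:

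- **That the rule can never trigger.** Cohort 2 patients who start ART before month 7 on CD4 or RNA grounds are taken off study, and 3.3.1 names those grounds. They are arguably already counted. Treating them as uncounted requires a filing choice that no text directs.
- **That the month-12 draw is a major gap.** The Precis allows 2 weeks either side and 3.5.2 allows 30 days. With confirmation 28 days later, a draw 14 days early is confirmed 14 days after month 12, and one 30 days early is confirmed 2 days before. The draw therefore bears on the current rule only at the extreme edge.
- **That the pooled limit shows undercounting.** It is merely redundant: 5 events across two cohorts force at least 3 in one.
- **That patients are left unprotected.** Section 3.7 stops dosing, 7.5.1 requires at least monthly data review with viral replication as a named item, and unanticipated problems go to the IRB within 7 days (7.3.1).

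**Conclusion.** The point holds as a defect in the trigger's wording. Read literally, 6.7 does not count patients who meet a confirmed CD4 or RNA criterion between about months 7 and 12, which is part of the period it says it covers. Whether it counts patients taken off study earlier under 3.3.1 is less clear.

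The size cannot be given as a probability, because the plan supplies no event rate, no accrual rate and no split of events by month. What can be shown is that the same patients can yield 3 under one reading and at most 1 under the other, on either side of the halt threshold. This assumes the literal reading is the one applied.

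The practical effect also depends on enrolment still being open. This version records that the IND was withdrawn in April 2018 and that sponsor monitoring has ended, but does not state accrual status. If enrolment has closed, only the reported count is affected.

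**What to change.** Keep the thresholds of 3 and 5 and the month-12 cutoff. Correct the references to 3.9, 3.9.7 and 3.9.8 so that they point to 3.7 and its 7th and 8th bullets. Replace the clause on removal with wording such as:

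> meet the section 3.7 CD4 or HIV-1 RNA criterion, confirmed as that section requires, before month 12. Each Cohort 1 or 2 patient counts once, regardless of vaccination status, on-study status, replacement or recorded exit reason.

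Dating an event by its first qualifying value, or ruling the month-12 draw in, would move the window. Those are optional design choices and not part of this correction.

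The cost is small. Appendix 2A already schedules CD4 and HIV-1 RNA at months 1, 2, 3, 6, 7 and 12; it should govern over 3.5.1.2, which omits RNA at months 2 and 6. A value first seen at month 7 needs an unscheduled confirmatory draw, which 3.7 already implies. For patients leaving under 3.3.1, the 3.8 evaluation within 8 weeks can confirm if it falls 4 weeks after the first value, although ART started in between may lower the RNA.

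The downside is a somewhat higher chance of a halt, including false ones. On the assumptions above, and if p is purely background risk, full counting reaches the threshold with probability 0.06 at 2% and 0.44 at 5%. A halt leads to IRB consultation, not automatic termination.

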- To characterize HPV and HIV knowledge and risk and sexual behaviors in the study cohort populations.

Eligibility:

Individual Cohorts

- Cohort 1: HIV-positive, CD4 cell count ≥ 350 cells/mm³, HIV-1 RNA level by RT PCR $\leq 20,000$ copies/ml, on stable HAART regimen for ≥ 6 months.
- Cohort 2: HIV-infected, CD4 cell count ≥ 500 cells/mm³, HIV-1 RNA level by RT PCR $\leq 20,000$ copies/ml, on no antiretroviral treatment.
- Cohort 3: healthy, HIV-negative controls

All Cohorts

- Females and males age 12 to 26 years
- Patients must have a hemoglobin ≥ 10.0 gm/dL, neutrophil count (ANC) $\geq 1500/\text{mm}^3$, platelet count $\geq 75,000/\text{mm}^3$ and PT or PTT $\leq 1.5X$ ULN (with the exception of patients with known clotting disorders or lupus anticoagulant); SGPT/SGOT $\leq 2/5X$ ULN, total bilirubin $\leq 1.5X$ ULN unless attributable to protease inhibitor therapy.

- Patients must test negative for hepatitis B virus and hepatitis C virus, unless the result is consistent with prior vaccination or prior infection with full recovery.
- No use of investigational agents within 4 weeks of study enrollment or use of immunosuppressive or immunomodulating agents within 8 weeks of study entry.

Study Design:

- This is a non-randomized, prospective, phase I study of quadrivalent human papillomavirus (types 6, 11, 16, 18) recombinant vaccine.
- The study includes 3 cohorts of pre-adolescents, adolescents and young adults 12-26 years of age as outlined under Eligibility Criteria. Each cohort will enroll 35 patients.
- All study subjects will receive three doses of HPV vaccine at 0, 2 and 6 months administered IM.
- Study participants will be monitored at months 0, 1, 2, 3, 6, 7 and 12 (\pm 2 weeks for each visit) and every 6 months (\pm 30 days) thereafter for 48 months total.

TABLE OF CONTENTS

PRECIS	2
TABLE OF CONTENTS	4
1 INTRODUCTION	7
1.1 Study Objectives	7
1.2 Background and Rationale.....	7
1.2.1 Human Papillomavirus (HPV) Infection	7
1.2.2 HPV Infection in Children.....	9
1.2.3 Adolescent Sexual Behavior and HPV Infection.....	10
1.2.4 HIV Infection and HPV Co-Morbidity	11
1.2.5 Quadrivalent Human Papillomavirus (types 6, 11, 16, 18) Recombinant Vaccine	13
1.2.6 Rationale for Study Cohort Population.....	15
2 ELIGIBILITY ASSESSMENT AND ENROLLMENT.....	16
2.1 Eligibility Criteria	16
2.1.1 Cohort 1 Inclusion and Exclusion Eligibility Criteria	16
2.1.2 Cohort 2 Inclusion and Exclusion Eligibility Criteria	17

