3.5.2 Follow-Up Study Visits Year 1: Months 1, 3, 7 (\pm 2 weeks) and 12 (\pm 30 days)

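### On the planned schedule, the section 6.7 accrual rule covers CD4 and HIV-1 RNA events first seen up to about 1 to 1.5 months after the vaccine series, not the 6 months it states

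*Combined protocol and SAP*

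**What the plan says.** Under section 6.7, accrual to Cohorts 1 and 2 is "halted if 3 or more patients within a given cohort or 5 or more total patients between the two cohorts" meet the condition. Patients meet it when they "are removed from the study before month 12 for a decline in CD4 count (3.9.7) and/or an increase in HIV-1 RNA levels (3.9.8"). The section justifies month 12 on the ground that "it includes 12 months of observation following the first HPV vaccination and 6 months of observation following completion of the vaccination series". It adds that events after month 12 most likely reflect antiretroviral resistance (Cohort 1) or the natural course of HIV disease (Cohort 2).

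The criteria themselves are in section 3.7. The CD4 criterion is a fall of more than 30% from baseline, or a "decrease in absolute CD4 count to < 350 cells/mm³ confirmed by at least 2 measurements 4 weeks apart". The viral load criterion reads "Off Treatment- Increase in HIV-1 RNA levels to > 100,000 copies/ml confirmed by at least 2 measurements 4 weeks apart". Both carry the off-treatment label only.

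On timing, the Precis states: "Study participants will be monitored at months 0, 1, 2, 3, 6, 7 and 12", with a window of 2 weeks for each visit. The heading of section 3.5.2 begins "Follow-Up Study Visits Year 1: Months 1, 3, 7", gives those visits 2 weeks, and gives month 12 a window of 30 days. For the HIV-infected cohorts, Appendix 2A marks CD4 and HIV-1 RNA at screening and at months 1, 2, 3, 6, 7 and 12. It shows nothing between months 7 and 12 and no confirmatory visit. The last vaccine dose is at month 6.

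**The concern.** The rule counts removals, removal needs a confirmed value, and confirmation takes 4 weeks. With no planned test between months 7 and 12, the month 12 value is the only scheduled look at the last five months of the stated window. Its confirmation normally falls after the window has closed. The measurement that is meant to supply most of the post-series observation therefore hardly contributes to the trigger.

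Two features of the plan make this matter. Section 7.5.1 concludes that neither an independent monitor nor a monitoring board is needed, and section 6.7 is the only numerical accrual-halt rule in the documents. Section 6.7 also supplies a presumption that later events have causes other than the vaccine. A change that arises in months 7 to 12 but is confirmed in month 13 would fall under that presumption, although it arose inside the period the rule says it watches.

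**Working it through.** **Inputs.** Doses at months 0, 2 and 6 (Precis). CD4 and HIV-1 RNA at months 1, 2, 3, 6, 7 and 12 (Appendix 2A). Confirmation interval of 28 days (section 3.7). Cutoff at month 12 (section 6.7). Month 12 window of 14 days (Precis) or 30 days (section 3.5.2). Cohort size 35. One month is taken as 365.25/12 = 30.44 days.

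**The plan's own figure.** 12 − 0 = 12 months after the first dose and 12 − 6 = 6 months after the last. Both reproduce as calendar intervals.

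**When an event first seen at the month 12 visit is confirmed.** Confirmation day = visit day + 28, against a cutoff at day 365.

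- Nominal visit: 365 + 28 = 393, which is 28 days late.
- Earliest visit under the 2-week window: 351 + 28 = 379, which is 14 days late.
- Earliest visit under the 30-day window: 335 + 28 = 363, which is 2 days early. Only a visit in about the first 2 days of that window, repeated at exactly 28 days, can count.

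With 30-day months the margins are the same: 28 days late, 14 days late and 2 days early.

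**Post-series coverage of first detections.**

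- The last scheduled test before month 12 is at month 7: 7 − 6 = 1 month after the series.
- If the month 7 visit is 2 weeks late: 1 + 14/30.44 = 1.46 months.
- The untested gap from month 7 to month 12 is 5 × 30.44 = 152 days, or 5 of the 6 months cited.
- Even with continuous testing, the 28-day repeat would limit countable first detection to day 365 − 28 = 337. That is (337 − 183)/30.44 ≈ 5.1 months after the series, so 6 is not reachable under this counting rule.

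The 1-month figure itself assumes that a qualifying month 7 value is repeated at about month 8, for which no visit is scheduled. If the repeat waits for the month 12 visit, that event would normally be lost to the count as well.

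**Illustration of the effect on the trigger.** The documents give no event rate, so this rests on assumptions: constant hazard, independent patients, the same risk p over 12 months in both cohorts, and full cohorts of 35. If only events arising by month 7 can count, the risk becomes q = 1 − (1 − p)^(7/12). The entries are binomial probabilities of reaching the threshold, first with all 12-month events counted and then with only those arising by month 7.

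| p | q | 3 or more of 35 | 5 or more of 70 |
|---|---|---|---|
| 5% | 2.95% | 0.25 → 0.08 | 0.27 → 0.06 |
| 10% | 5.96% | 0.69 → 0.35 | 0.84 → 0.41 |
| 20% | 12.21% | 0.98 → 0.82 | 1.00 → 0.94 |

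**The case against.** The best defence is that section 6.7 does not speak with one voice. Its operative sentence counts removals, but the next sentence refers to the events occurring before month 12, and the rationale plainly treats the month 12 visit as part of the window. Dating by occurrence is a plausible intention. This stands as a reading of intent. It does not rescue the text, because the sentence that sets the trigger counts removals and nothing says how an event first seen at the month 12 visit is handled.

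Second, section 3.7 asks only that a change be "confirmed by at least 2 measurements 4 weeks apart" and does not limit those measurements to study visits. Section 3.3.1 has the referring physician manage antiretroviral changes with the protocol team, so an unscheduled test could reveal an event earlier. That is possible, but the protocol plans no such test.

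Third, a reader might infer that late events can never count, or that the trial is blind to late harm and discards it. The documents do not support this. The 30-day window leaves the narrow exception shown above. Section 6.3 follows HIV-1 RNA up to 1 year and lists day 1 against month 12 as a timepoint. Section 7.5.1 has clinical, laboratory and adverse event data reviewed at least monthly. The criteria in 3.7 have no month 12 limit. Section 6.7 calls other causes of later events most likely; it does not say that those events are ignored.

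Finally, the documents give neither an event rate nor an accrual rate. How often the trigger would change, and whether accrual would still be open when patients reach month 12, cannot be determined. If accrual has closed, the halt is moot, but the attribution of events around month 12 is not.

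**Conclusion.** The point holds as a mismatch between the counting rule and its stated rationale. On the planned schedule, an event arising after the month 7 visit will almost never be confirmed in time to count. The rule covers first detections up to about 1 to 1.5 months after the series instead of 6. This rests on reading the rule literally as removals before month 12, on the schedule in Appendix 2A, and on a prompt repeat of any qualifying month 7 value. It does not depend on the month convention. Under the Precis window there is no scheduled exception; under the section 3.5.2 window there is one of about 2 days.

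The gap lies in one formal accrual trigger and is not a loss of safety observation. The trigger probabilities above show a direction and a possible size under assumed risks; they are not estimates for this trial.

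The same sentence has a second defect that affects whether the rule can be operated at all. Section 6.7 counts patients removed from the study, while section 3.7 labels both criteria as off treatment only, and no vaccine dose remains after month 6. Section 6.7 also cites 3.9, 3.9.7 and 3.9.8, which do not exist in this protocol.

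**What to change.** In section 6.7, date each event by its first qualifying value. Suggested wording: *A patient counts towards this rule if the first qualifying CD4 or HIV-1 RNA value is obtained at or before the month 12 visit and is subsequently confirmed as section 3.7 requires, whether or not the confirmation falls after month 12.* Tying the rule to the visit avoids relying on either of the two stated windows. If the sponsor prefers to keep the count of removals before month 12, the rationale should instead give the post-series observation as about 1 month.

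In the same edit, the sponsor should reconcile:

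- removal from the study (6.7) with the off-treatment label (3.7);
- the references to 3.9, 3.9.7 and 3.9.8 with the section that holds the criteria;
- the month 12 window, which is 2 weeks in the Precis and 30 days in 3.5.2.

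The cost is one or two sentences plus these corrections. No clinical threshold or scheduled visit changes, and the repeat measurement is already required by 3.7. The downside is that the final count for a patient may come about a month later.
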